APPENDIX IV: ANTICIPATED ADVERSE EVENTS

1. Incidence of anticipated adverse events with the HM3, HM2 and HVAD at 2 years from Pivotal Trials and Real-World Data from the INTERMACS Database

Anticipated Adverse Events	% of Subjects with Events		
	HEARTMATE 3	HEARTMATE II	HVAD
All-cause Death	HM3 CE MARK ⁵ : 24% MOMENTUM 3 ¹¹ : 19% INTERMACS 2019 ¹² : 16.0%	ENDURANCE: 32.2% MOMENTUM 3 ¹¹ : 19.7% INTERMACS 2019: 28.0%	ENDURANCE ¹³ : 39.2% INTERMACS 2019: 28.0%
Bleeding	HM3 CE MARK: 50% MOMENTUM 3: 43.7%	ENDURANCE: 60.4% MOMENTUM 3: 55.0%	ENDURANCE: 60.1%
Stroke	HM3 CE MARK: 24% MOMENTUM 3: 9.9% INTERMACS 2019: 7.0%	ENDURANCE: 12.1% MOMENTUM 3: 19.4% INTERMACS 2019: 18%	ENDURANCE: 29.7% INTERMACS 2019: 22.0%
Infection	INTERMACS 2019: 41.0%	INTERMACS 2019: 51.0%	INTERMACS 2019: 55.0%
Driveline	HM3 CE MARK: 24% MOMENTUM 3: 23.3%	ENDURANCE: 15.4% MOMENTUM 3: 19.4%	ENDURANCE: 19.6%
Sepsis	HM3 CE MARK: 22% MOMENTUM 3: 15.1%	ENDURANCE: 15.4% MOMENTUM 3: 14.9%	ENDURANCE: 23.6%
Suspected/Confirmed PT	HM3 CE MARK: 0.0% MOMENTUM 3: 1.4%	ENDURANCE: 10.7% ^a MOMENTUM 3: 13.9%	ENDURANCE: 6.4% ^a
Cardiac Arrhythmia	HM3 CE MARK ^b : 34% MOMENTUM 3: 35.9%	ENDURANCE: 40.9% MOMENTUM 3: 41.0%	ENDURANCE: 37.8%
Right Heart Failure	HM3 CE MARK: 14% MOMENTUM 3: 34.2% INTERMACS 2019: 37.0%	ENDURANCE: 26.8% MOMENTUM 3: 28.3% INTERMACS 2019: 34.0%	ENDURANCE: 38.5% INTERMACS 2019: 46%
Renal Dysfunction	HM3 CE MARK ^b : 10% MOMENTUM 3: 14.2%	ENDURANCE: 12.1% MOMENTUM 3: 11.1%	ENDURANCE: 14.9%
Hepatic Dysfunction	HM3 CE MARK ^b : 2.0% MOMENTUM 3: 4.9%	ENDURANCE: 8.1% MOMENTUM 3: 5.3%	ENDURANCE: 4.7%
Respiratory Failure	HM3 CE MARK ^b : 16.0% MOMENTUM 3: 21.6%	ENDURANCE: 25.5% MOMENTUM 3: 19.4%	ENDURANCE: 29.1%
Hypertension	HM3 CE MARK ^b : 2.0% MOMENTUM 3 ^d : 8.2%	ENDURANCE: 16.8% MOMENTUM 3 ^d : 9.3%	ENDURANCE: 15.9%
Pericardial Fluid Collection	HM3 CE MARK ^b : 2.0% MOMENTUM 3 ^d : 4.9%	ENDURANCE ^c : 6.0% MOMENTUM 3 ^d : 8.7%	ENDURANCE ^c : 2.7%
MI	HM3 CE MARK ^b : 0.0% MOMENTUM 3 ^d : 1.2%	ENDURANCE ^c : 0% MOMENTUM 3 ^d : 1.0%	ENDURANCE ^c : 1.4%
Hemolysis	HM3 CE MARK: 0.0% MOMENTUM 3 ^d : 1.2%	ENDURANCE: 8.7% MOMENTUM 3 ^d : 1.6%	ENDURANCE: 8.1%

This confidential document is the property of Abbott and shall not be reproduced, distributed, disclosed or used without the express written consent of Abbott

Post Market Surveillance Plan

Arterial Non-CNS TE	HM3 CE MARK ^b : 0.0% MOMENTUM 3 ^d : 1.0%	ENDURANCE: 6.7% MOMENTUM 3 ^d : 2.0%	ENDURANCE: 6.1%
Venous TE	HM3 CE MARK ^b : 0.0% MOMENTUM 3 ^d : 3.9%	ENDURANCE ^c : 3.4% MOMENTUM 3 ^d : 2.8%	ENDURANCE ^c : 2.7%

PT – pump thrombosis; TE – thromboembolic events; MI – myocardial infarction; Non-CNS – non central nervous system.

Pivotal study sample size: HM3 CE MARK: 50 patients implanted with the HM3; MOMENTUM 3: 1028 (8 patients died post randomization; data reported are from 515 HM3 and 505 HM2 patients); ENDURANCE: 446 (1 patient did not receive either device; data reported are from 296 HVAD and 149 HM2 patients).

^a Pump thrombosis requiring pump exchange.

^{b, c, d} From clinicaltrials.gov (NCT02170363, NCT01166347 and NCT02224755).

2. Device issues identified and addressed during MOMENTUM3 IDE study

Outflow graft twist

At the time this issue was identified, 35 of 5607 (0.62%) devices implanted worldwide were reported to have this issue. The outflow graft (OG) twist resulted in low blood flow and/or formation of thrombus within the OG. There were three deaths that were attributed to this issue. On May 22nd, 2018, the FDA categorized this as a Class I recall event. Analysis done by the Sponsor suggested that, over time, normal motion such as the heart beating, respiration and patient activity can cause small rotations between the OG bend relief component and the outflow graft metallic connector underneath. These forces, known as “in vivo loads”, are believed to cause the OG twisting. Additionally, it was determined that the twisting may occur more easily if the screw ring is not firmly hand tightened during implant. In response to the identification of this issue, initially a clip was designed to secure the OG to the pump housing and then later the pump housing design was modified to prevent the OG twist from occurring.

HM3 Driveline Communication Fault

On June 7, 2017, the Sponsor notified the MOMENTUM 3 DSMB chair and investigators of limited reports of errors in communication between the System Controller and pump of the HM3 LVAS. The root cause of the errors was traced to manufacturing variances from a single supplier that could lead to crystallization within the pump electronics.

The specifications and manufacturing processes for the HM3 pump have been updated to ensure this issue did not occur in future lots. In addition, the Sponsor retrieved potentially impacted HM3 implant kits from hospital shelves. The units that were removed from investigational sites were replaced with product not impacted by this field advisory.

To date, there have been no adverse effects related to this issue; however, it may lead to frequent advisory alarms that may need to be silenced. In the notification to investigators, the Sponsor provided recommendations for managing patients with advisory alarms. The Sponsor has received acknowledgment forms from all investigators indicating that they were made aware of the issue and the associated recommendations.

Post Market Surveillance Plan

APPENDIX V: CASE REPORT FORMS

Final draft CRFs will be sent under a separate cover.

Post Market Surveillance Plan

APPENDIX VI: INFORMED CONSENT FORM

A template informed consent form will be provided under a separate cover.

Post Market Surveillance Plan

APPENDIX VII: MONITORING PLAN

A copy of the Monitoring Plan can be obtained upon request from the Sponsor Clinical Project Manager for the post market surveillance.

Post Market Surveillance Plan

APPENDIX VIII: REVISION HISTORY

This PMS plan may be amended as appropriate by the Sponsor. Rationale will be included with each amended version in the revision history table below. The version number and date of amendments will be documented.

IRB and relevant Regulatory Authorities, if applicable, will be notified of amendments to the PMS plan.

Amendment Number	Version	Date	Details	Rationale
Not Applicable	A	02/DEC/2020	First release of PMS plan	NA

Post Market Surveillance Plan

APPENDIX IX: PMS PLAN SUMMARY

Post Market Surveillance Study Name and Number	Hong Kong and Taiwan HM3 PMS CRD_1022
Title	Post Market Surveillance of the HeartMate 3 Left Ventricular Assist System in Hong Kong and Taiwan
Primary Objective	
The primary objective of this prospective, post-market surveillance study is to assess the use of the HM3 LVAS in the setting of Hong Kong and Taiwanese standard-of-care for advanced heart failure patients implanted with this device.
 
Secondary objective of this PMS is to assess the adverse events occurring during the surveillance period.
 
Assessments will include: 6-minute walk test, New York Heart Association heart failure severity classification, EQ-5D-5L quality of life questionnaire, rates of survival, transplant, pump explant or exchange, device malfunctions, reoperations, rehospitalizations and incidence of adverse events including, but not limited to, neurological dysfunction, bleeding, device thrombosis, and infection.

Device Under Investigation	HeartMate 3™ Left Ventricular Assist System
Number of Subjects Required for Inclusion in Post market surveillance	All consecutive patients at the participating sites with a planned HM3 implant, that meet the HM3 commercially approved labelling indications are eligible to participate in this PMS. We expect approximately 30 patients will be enrolled during the surveillance period.
Post market surveillance Design	Prospective, single arm, open-label, multi-center, post market surveillance study
Subject Follow-up	
Surveillance visits will occur at:
 
 • Baseline/Enrollment (prior to HM3 implant) • HM3 Implant • Month 1 ± 7 days • Month 3 ± 30 days • Month 6 ± 30 days • Month 12 ± 30 days • Month 24 ± 60 days 
Note:
 
 – The follow-up visits are relative to the date of HM3 implant. – A month is defined as 30 days. – the patients will be followed until they experience an outcome or the 24 month follow-up visit is completed, whichever comes first.

Post Market Surveillance Plan

## Statistical Analysis Plan

### 1.0 SYNOPSIS OF STUDY DESIGN

#### 1.1 Purpose of the Statistical Analysis Plan

This statistical analysis plan (SAP) is intended to provide a detailed and comprehensive description of the planned methodology and analysis to be used for CIP 10382, the Post Market Surveillance (PMS) of the HeartMate 3 Left Ventricular Assist System in Hong Kong and Taiwan. This plan is based on the Version A, Dec 2, 2020 Clinical Investigation Plan (CIP).

#### 1.2 Clinical Investigation Objectives

The primary objective of this PMS is to collect data on clinical and functional outcomes of the HeartMate 3™ (HM3) left ventricular assist system (LVAS) as a treatment for advanced heart failure, refractory to optimal medical management in Hong Kong and Taiwan.

#### 1.3 Clinical Investigation Design

This is a prospective, single arm PMS which will enroll approximately 30 patients that meet the PMS Inclusion/Exclusion criteria, from approximately 4 sites in Hong Kong and Taiwan.

The surveillance period for this PMS is 24 months and follow-up visits will occur at Baseline/ Enrollment, HM3 Implant, 1, 3, 6, 12 and 24 months. All subjects will be followed from enrollment through the end of the 24 months surveillance period or occurrence of an outcome, whichever is earlier. Outcomes include Transplant, Explant, Exchange, Withdrawn or Death.

### 1.4 Endpoints

#### 1.4.1 Primary Efficacy Endpoint

Primary efficacy endpoint is defined as the overall survival to transplant, myocardial recovery or on device support free of debilitating stroke (Day 60 Modified Rankin Score >3) or reoperation for pump replacement during the 24 months surveillance period. Subjects who are urgently transplanted due to a HM 3 malfunction prior to 24 months will be considered to have experienced a primary endpoint event, as will subjects who expire, suffer a debilitating stroke or have their HM3 exchanged due to a device failure prior to 24 months.

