6.5 Subject Outcomes

Subjects will be followed until the 24-month follow-up is completed or until they experience an outcome, whichever occurs first. Outcomes include death, heart transplantation, HM3 exchange or explant, and withdrawal from the PMS. Outcomes must be reported to the Sponsor through the EDC system immediately upon discovery of the event.

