6.6 Schedule of Events

All of the post market surveillance assessments and their schedule are listed in **Table 5**.

This confidential document is the property of Abbott and shall not be reproduced, distributed, disclosed or used without the express written consent of Abbott

Post Market Surveillance Plan

Table 5. Schedule of assessments.

Assessment	Baseline/ Enrollment	HM3 Implant	Month 1 ¹ (± 7 days)	Month 3 ¹ (± 30 days)	Month 6 ¹ (± 30 days)	Month 12 ¹ (± 30 days)	Month 24 (± 60 days)	As Occurs or Unscheduled
Eligibility Assessment	X							
Informed Consent	X							
Demographics	X							
General and Cardiac Medical History	X							
Right Heart Catheterization	X ²							X ²
HM3 Information		X						X ³
Implant Data		X						X ³
Vital Signs	X		X	X	X	X	X	X
Laboratory Assessments	X		X	X	X	X	X	X
Echocardiogram	X ²		X ²	X ²	X ²	X ²	X ²	X ²
Medications	X		X	X	X	X	X	X
Functional Capacity	X		X	X	X	X	X	X ²
EQ-5D-5L Quality of Life Questionnaire	X		X	X	X	X	X	X ²
Pump Parameters		X	X	X	X	X	X	X
Subject Status			X	X	X	X	X	X
Subject Outcome								X
Rehospitalizations								X
Adverse Events								X
Device Deficiencies ^{4,5}								X
Modified Rankin Score (MRS) Assessment ⁶								X
Reoperations (excluding primary implant)								X
Protocol Deviations	X	X	X	X	X	X	X	X
COVID-19 questions (if applicable)	X	X	X	X	X	X	X	X

Note: Patients will be followed until the 24 months visit or they experience an outcome, whichever comes first.

¹One month = 30 days.

²If performed as standard of care.

³Implant data for HM3 to HM3 exchange(s) and only relevant information for non-HM3 exchange.

⁴Device deficiencies that result in adverse events only. Please see section 7.3.2 for further information.

Post Market Surveillance Plan

Assessment	Baseline/ Enrollment	HM3 Implant	Month 1 ¹ (± 7 days)	Month 3 ¹ (± 30 days)	Month 6 ¹ (± 30 days)	Month 12 ¹ (± 30 days)	Month 24 (± 60 days)	As Occurs or Unscheduled
------------	-------------------------	-------------	------------------------------------	-------------------------------------	-------------------------------------	--------------------------------------	-------------------------	-----------------------------

⁵Device malfunction is included within the definition of Device Deficiency.

⁶ Required only if a stroke has occurred

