8.2.1 Primary Efficacy Endpoint

Primary efficacy endpoint is defined as the overall survival to transplant, myocardial recovery or on device support free of debilitating stroke (Modified Rankin Score >3) or reoperation for pump replacement during the 2-year surveillance period; this will be assessed using the Kaplan-Meier product-limit method along with a competing outcomes graph. Subjects who are urgently transplanted due to a HeartMate 3 malfunction will be considered to have experienced a primary endpoint event, as will subjects who expire, suffer a debilitating stroke or have their HeartMate 3 exchanged due to a device failure. Subjects who are transplanted (except as described above), explanted for recovery, withdraw from the trial or are lost to follow-up will be censored at that time in the analysis.

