Any new, temporary or permanent, focal or global neurological deficit, ascertained by a standard neurological history and examination administered by a neurologist or other qualified physician and documented with appropriate diagnostic tests and consultation note; or an abnormality identified by surveillance neuroimaging. The examining physician will classify the event as defined below:

- Transient ischemic attack*, defined as an acute transient neurological deficit conforming anatomically to arterial distribution cerebral ischemia, which resolves in < 24 hours and is associated with no infarction on brain imaging (head CT performed >24 hours after symptom onset; or MRI)
- Ischemic Stroke*: a new acute neurologic deficit of any duration associated with acute infarction on imaging corresponding anatomically to the clinical deficit, or a clinically covert ischemic stroke seen by surveillance imaging, without clinical findings of stroke or at the time of event recognition.
- Hemorrhagic Stroke*: a new acute neurologic deficit attributable to intracranial hemorrhage (ICH), or a clinically covert ICH seen by surveillance imaging, without clinical findings of ICH at the time of event recognition.
- Encephalopathy: Acute new encephalopathy** due to hypoxic-ischemic injury (HIE), or other causes, manifest as clinically evident signs or symptoms, or subclinical electrographic seizures found by complete neurological diagnostic evaluation to be attributable to acute global or focal hypoxic, or ischemic brain injury not meeting one of ischemic stroke or ICH events as defined above.
- Seizure of any kind
- Other neurological event (non-CNS event): examples include neuro muscular dysfunction or critical care neuropathy

*Modified Rankin Score will be used to classify the severity of all strokes

**Acute encephalopathy is a sign or symptom of some underlying cerebral disorder and is manifest as depressed consciousness with or without any associated new global or multifocal neurologic deficits in cranial nerve, motor, sensory, reflexes and cerebellar function.

11. Psychiatric Episode

Disturbance in thinking, emotion or behavior that causes substantial impairment in functioning or marked subjective distress requiring intervention. Intervention is the addition of new psychiatric medication or hospitalization. Suicide is included in this definition.

12. Renal Dysfunction

Two categories of renal dysfunction will be identified:

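### The stroke part of the primary endpoint has no time point in the protocol but is fixed at Day 60 in the SAP, and a severe stroke without a Day 60 score then counts as a non-event

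*SAP*

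**What the plan says.** **Definition.** Protocol 8.2.1 requires survival "free of debilitating stroke (Modified Rankin Score >3) or reoperation for pump replacement during the 2-year surveillance period". SAP 1.4.1 requires survival "free of debilitating stroke (Day 60 Modified Rankin Score >3) or reoperation for pump replacement during the 24 months surveillance period". The threshold is the same. Only the SAP names a day, and it gives neither the starting point of the count nor any note that it departs from the plan.

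**Version.** SAP 1.1 says it rests on Version A of 2 December 2020. Protocol Appendix VIII lists that version alone, described as "First release of PMS plan". Both texts are therefore current.

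**Collection of the score.** Protocol Table 5 (section 6.6) lists mRS only in the as-occurs column, with the footnote "Required only if a stroke has occurred". Appendix II adds: "Modified Rankin Score will be used to classify the severity of all strokes". Neither gives a day. Table 3, the list of follow-up assessments, has no mRS, and visits are counted from implant (section 6.3). On the forms, Appendix V says: "Final draft CRFs will be sent under a separate cover".

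**Follow-up and censoring.** Protocol 6.5 states: "Subjects will be followed until the 24-month follow-up is completed or until they experience an outcome, whichever occurs first". Outcomes there include transplant, exchange, explant and withdrawal. After withdrawal only vital status is recorded (protocol 5.5). SAP 2.2.3 censors anyone who has not met the SAP 1.4.1 definition at elective transplant, explant for recovery, withdrawal, loss to follow-up or 24 months, whichever is first. SAP 2.8 allows no imputation apart from the six-minute walk rule.

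**The concern.** The same subject can be a primary event under one document and a non-event under the other. Two kinds of survivor are affected: one whose mRS is above 3 soon after the stroke and 3 or lower by Day 60, and one whose early mRS is above 3 and who has no Day 60 score.

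The second kind matters more, because it can arise with no protocol deviation. A site that records one mRS at stroke onset has done what Table 5 asks, yet has supplied nothing that the SAP definition can use. A stroke followed within 60 days by elective transplant, explant for recovery or withdrawal, or one less than 60 days before the final visit, also need not have the score. Leaving a severe stroke out of the primary endpoint in these cases should be a deliberate choice, made before the strokes are known.

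**Working it through.** The plan gives no figure to reproduce: there is no formal sample size calculation and the endpoints are not powered. The check sets the definitions side by side and then sizes one reclassified subject.

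**1. Anchor of Day 60.** With 30-day months (protocol 6.3), the Month 1 window is days 23 to 37 after implant (30 ± 7) and the Month 3 window is days 60 to 120 (90 ± 30). Counted from implant, Day 60 would fall on the first day of the Month 3 window, where no mRS is scheduled, and could not score a later stroke. Sixty days after the stroke is the only workable reading, but it is not written down.

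**2. Classification of a subject alive after a stroke, with no other primary event**

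| Post-stroke mRS | Protocol 8.2.1 | SAP 1.4.1 with 2.2.3 and 2.8, read literally |
|---|---|---|
| Never above 3 | Not an event | Not an event |
| Above 3 early and at Day 60 | Event | Event |
| Above 3 early, 3 or lower at Day 60 | Can be read as an event | Not an event |
| Above 3 early, no Day 60 score | Can be read as an event | Not an event; censored at the listed time |

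Only the last two rows differ. Deaths are events in both documents.

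**3. Effect of one reclassified subject on the 24-month Kaplan-Meier estimate.** Inputs: N = 30 (approximate enrolment, protocol 5.6) and no other censoring.

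- *Event versus event-free to 24 months.* With m other events, the estimates are (29 − m)/30 and (30 − m)/30. The difference is 1/30 = 3.3 points for any m.
- *Event versus censored.* Let d be the number of other events before the subject's censoring time and k the number after it. As an event, the estimate is (29 − d − k)/30. As censored, it is [(30 − d)/30] × [(29 − d − k)/(29 − d)]. The difference is (1/30) × (29 − d − k)/(29 − d). HM3 two-year deaths in Appendix IV of 16.0%, 19% and 24% give 30 × 0.16 = 4.8, 30 × 0.19 = 5.7 and 30 × 0.24 = 7.2, so k = 5, 6 and 7 are used with d = 0:
  - k = 5: (1/30) × 24/29 = 2.8 points
  - k = 6: (1/30) × 23/29 = 2.6 points
  - k = 7: (1/30) × 22/29 = 2.5 points
- *Another primary event before 24 months.* The subject is one event either way, so the difference at 24 months is zero.

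Earlier censoring of other subjects enlarges the step. If 10 subjects (an assumption) were censored before the first event, 1/30 would become 1/20 = 5.0 points.

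**4. Will the rule be needed?** Appendix IV gives HM3 two-year stroke rates, of any severity, of 7.0%, 9.9% and 24%. Expected subjects with a stroke: 30 × 0.07 = 2.1, 30 × 0.099 = 3.0, 30 × 0.24 = 7.2. The chance of at least one, 1 − (1 − p)^30, is 89%, 96% and more than 99.9%. A stroke will probably have to be classified. The documents do not give the share of survivors whose early mRS exceeds 3 and who improve or go unscored, so the number reclassified cannot be computed.

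**The case against.** The strongest reply is that the SAP already settles the matter. SAP 2.2.3 is a residual rule: whoever has not met the definition is censored at the listed time, so an unscored stroke need not be named. A reader might infer from the missing score that such a subject has no classification at all. The documents do not support that, since the literal reading gives one. What remains is that the rule is not explicit for this case, and its result is that a severe unscored stroke drops out of the endpoint.

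Second, Day 60 may be a refinement of a protocol that is silent on timing. That is fair, and the conflict does depend on reading the protocol to include an early score. But the day decides who is an event, and the plan's schedule was not written to deliver it.

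Third, the stroke form might ask for a Day 60 score. This stands as a limit: one should not infer that no mRS is collected, or that none is requested at Day 60, only that the plan requires none on that day. A form with the field would not settle the difference in definition or the handling of a missing score.

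Fourth, the stakes are modest. The endpoint is descriptive and unpowered (note to SAP 1.4.3), there is no success criterion (SAP 2.6), and strokes are also reported as percent of subjects and events per patient-year (SAP 2.2.4). This limits the severity but does not justify two definitions of the primary endpoint.

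A reader might also fear that the visit-window exclusion in SAP 2.8 would discard event-driven scores. That rule most naturally refers to the scheduled windows in protocol Table 4. An as-occurs mRS has no window, so no change to SAP 2.8 is needed.

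**Conclusion.** The point holds. The protocol and SAP define the stroke component differently, the plan requires no mRS on the day the SAP uses, and the literal SAP rules turn a severe stroke without that score into a non-event that the protocol wording can count as an event.

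The 24-month shifts of 3.3, 2.5 to 2.8 and zero points per reclassified subject rest on 30 subjects and no other censoring. It would be wrong to infer that every reclassification moves the estimate by 3.3 points, or that the 7.0% to 24% stroke rates measure the distortion. Those rates cover strokes of any severity, including fatal and mild ones that both documents classify alike. This should be fixed before database lock, but it threatens no hypothesis test or success decision.

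**What to change.** Use one definition in protocol 8.2.1 and SAP 1.4.1 before database lock, by one of two routes:

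- **Drop Day 60** from SAP 1.4.1 and state which post-stroke mRS counts.
- **Keep Day 60**, anchor it to stroke onset, date the event at stroke onset, and state in SAP 2.2.3 that a stroke without a Day 60 score is classified by the latest available post-stroke mRS. Confirm that the stroke case report form asks for the Day 60 score.

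The cost is a short SAP amendment and a change of protocol wording, with the IRB notification or approval that protocol 10.2 and 12.1 require. If Day 60 is kept and the form lacks the field, add one form field and one short assessment in the few subjects with a stroke (about 2 to 7 at the Appendix IV rates).
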